### **2.2 Secondary Objectives**

- 2.2.1 To determine the time to culture-conversion of the Moxifloxacin regimen and the Ethambutol regimen using data from 2-, 4-, 6-, and 8-week cultures
- 2.2.2 To compare the proportion of patients with any Grade 3 or 4 adverse reactions
- 2.2.3 To compare adverse events and 2-month culture conversion rates among HIV-infected patients vs. HIV-uninfected patients
- 2.2.4 To compare the rates of treatment failure and recurrence of the Intervention and Control arm.
- 2.2.5 To compare TB cure rates at month 6 and at end of TB treatment between the Intervention and Control Arm

### **2.3 Ancillary Objectives**

- 2.3.1 To determine if the LAM antigen test is an appropriate diagnostic test for TB suspects
- 2.3.2 To determine the effect of the drug concentration and pharmacokinetic/pharmacodynamic (PK/PD) parameters of Moxifloxacin and Rifampicin containing TB therapy on TB treatment outcomes (including but not limited to sputum culture conversion rates)
- 2.3.3 To determine the extent of the drug interaction between Moxifloxacin and Rifampicin containing TB treatment, and the clinical relevance of this interaction.
- 2.3.4 To determine the presence of specific polymorphisms of drug metabolizing enzymes and investigate the effect of these on Moxifloxacin and Rifampicin containing TB drug concentrations (including but not limited to polymorphisms of MDR1, SGT and UGT genotypes).
- 2.3.5 To determine the effect of Moxifloxacin and Rifampicin containing TB drug concentrations on drug resistance.
- 2.3.6 To assess the effect of relevant covariates on Moxifloxacin and Rifampicin containing TB drug concentrations

- 2.3.7 To assess acceptability and feasibility of short messaging service (sms) reminders amongst participants with recurrent tuberculosis enrolled in a clinical trial in an urban setting in Durban, South Africa
- 2.3.8 Using computerised dispensing to generate missed visit reports and other data that will be combined with cellular phone technology to assist with monitoring patient adherence, tracking and retention
- 2.3.9 Identify and validate correlates of risk of TB disease, recurrent TB disease and/or protection against recurrent TB induced by the novel TB vaccine candidate, ID93 + GLA-SE

### 3.0 STUDY DESIGN AND SETTING

This is an open label randomized controlled clinical trial comparing two regimens for treatment of smear-positive pulmonary TB, among patients previously treated for TB. Patients will be randomized to receive one of the two TB retreatment regimens as listed below. In the Intervention Arm, Moxifloxacin will be substituted for Ethambutol. “Study drugs” refer to all the drugs listed in Table 1.

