## SCHEMA

**Design:** This is an open label randomized controlled clinical trial comparing two regimens for treatment of smear-positive pulmonary TB, among patients previously treated for TB. The primary objective is to determine if a Moxifloxacin-containing regimen, substituting Moxifloxacin for Ethambutol, of 24 weeks duration is superior to a control regimen of 24 weeks duration in improving treatment outcomes in patients with recurrent TB.

**Duration :** Intervention Arm : Approximately 6 months treatment + 12 months post treatment follow up

Control Arm : Approximately 6 months treatment + 12 months post treatment follow up

**Sample Size:** 330

**Population :** This study will include adults 18 years and over with a previous history of TB. HIV infected and uninfected patients will be included in the study as well as patients on ARVs provided that these are not contra-indicated with any of the study drugs. Patients with *M tuberculosis* resistance to Rifampicin will be excluded at screening using Gene Xpert technology.

**Randomization:** Patients will be randomized to receive 1 of 2 TB retreatment regimens

[figure not shown]

Figure 1 : IMPRESS patient screening and randomization arms

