## **2.0 STUDY AIMS AND OBJECTIVES**

### **2.1 Primary objective**

The primary objective is to determine if a Moxifloxacin-containing regimen, [Isoniazid (H), Rifampicin (R), Pyrazinamide (Z), Moxifloxacin (M)], substituting Moxifloxacin for Ethambutol, of 24 weeks duration is superior to a control regimen [Isoniazid (H), Rifampicin(R), Pyrazinamide (Z), Ethambutol (E)] of 24 weeks duration in improving treatment outcomes in patients with recurrent TB.

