## 6.0 STUDY TREATMENT

### 6.1 Regimens, Administration and Duration

Once randomized to either the Control or Intervention arms the study drug is to be self-administered once daily before meals. Treatment should be commenced no more than 3 days after randomization. The Control and Intervention arms will follow the South African National Tuberculosis dosing guidelines for re-treatment cases as closely as possible. All patients will receive pyridoxine 50mg daily whilst in the study.

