**Table 2: Study drug regimens and duration: Control arm**

Pre-treatment body weight  (kg)	Intensive phase 7 days a week for 8 weeks  (56 doses)	Continuation phase – 7 days a week for 16 weeks  (112doses)	
	RHZE (150,75,400,275 mg)	RH (150,75 mg)	RH (300,150mg)
30-37	2 tabs	2 tabs	
38-54	3 tabs	3 tabs	
55-70	4 tabs		2 tabs
>71	5 tabs		2 tabs

H – Isoniazid; R – Rifampicin; Z – pyrazinamide; E – Ethambutol

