**Table 3: Study drug regimens and duration: Intervention arm**

Pre-treatment body weight	Intensive phase 7 days a week for 8 weeks (56 doses)				Continuation phase – 7 days a week for 16 weeks (112 doses)				
	(kg)	RH (150,75mg)	RH (300,150mg)	Z (500mg)	M (400mg)	RH (150,75mg)	M (400mg)	RH (300,150mg)	M (400mg)
30-37	2 tabs		2 tabs	1 tab	2 tabs	1 tab			
38-54	3 tabs		3 tabs	1 tab	3 tabs	1 tab			
>55		2 tabs	4 tabs	1 tab			2 tabs	1 tab	

H – Isoniazid; R – Rifampicin; Z – pyrazinamide, M - Moxifloxacin

In this study the total duration of TB therapy will be 24 weeks for the intervention arm, and the control arm. The duration of TB treatment may be extended depending on the time to sputum conversion.

In this study the total duration of TB therapy will be 24 weeks for the Intervention arm, and for the Control arm. The duration of TB treatment may increase due to a delay in the time to sputum conversion. This will result in the extension of TB treatment beyond 6 months. The required number of doses must be completed by the patient for the intensive phase of TB treatment before the patient can initiate the continuation phase of TB treatment. The study pharmacist and study clinician will monitor the number of doses ingested, by pill count, for each phase of treatment. The patient’s weight will be assessed monthly and the dose of the study product will be adjusted in accordance with the patient’s weight which will be assessed monthly.

In addition to the 6 months of TB treatment regimen, patients in the Intervention Arm, who provide informed consent to take part in the PK sub-study may be requested to take a single dose of Moxifloxacin 400mg, at the Month 7 visit (or subsequent visit if Month 7 visit has been missed). This PK sample for single dose moxifloxacin may be deferred to month after TB treatment completion on participants who have TB treatment extended beyond 6 months

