## 2. STUDY DESIGN

This is an open label randomized controlled clinical trial comparing two regimens for treatment of smear-positive pulmonary TB, among patients previously treated for TB. The primary objective is to determine if a Moxifloxacin-containing regimen, substituting Moxifloxacin for Ethambutol, of 24 weeks duration is superior to a control regimen of 24 weeks duration in improving treatment outcomes in patients with recurrent TB.

This study will include adults 18 years and over with a previous history of TB. HIV infected and uninfected patients will be included in the study as well as patients on ARVs provided that these are not contra-indicated with any of the study drugs. Patients with M tuberculosis

resistance to Rifampicin will be excluded at screening using Gene Xpert technology. A maximum of 330 participants will be included in the study.

Patients will be randomized in a 1:1 ratio to receive one of the two TB retreatment regimens, as outlined in the table below.

|                         | Intensive Phase (2 months) | Continuation Phase |
|-------------------------|-----------------------------------|---------------------------|
| Intervention Arm | HRZM* daily (2 months)            | HRM* daily (4 months)     |
| Control Arm      | HRZE* daily (2 months)            | HR* daily (4 months)      |

\* Isoniazid (H), Rifampicin (R), Pyrazinamide (Z), Moxifloxacin (M), Ethambutol (E)

The duration of TB treatment may increase due to a delay in the time to sputum conversion which will result in the extension of TB treatment beyond 6 months. Following treatment, participants will be followed up on a two-monthly basis for 12 months.

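### The doses in Tables 2 and 3 and the HRM v HR continuation phase go beyond a moxifloxacin-for-ethambutol swap, so a between-arm difference cannot be attributed to the substitution alone

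*Protocol*

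**What the plan says.** Four places describe the contrast as an exchange of one drug:

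- Protocol 3.0: "In the Intervention Arm, Moxifloxacin will be substituted for Ethambutol".
- Protocol Schema: "substituting Moxifloxacin for Ethambutol, of 24 weeks duration is superior to a control regimen of 24 weeks duration".
- Protocol 2.1: "substituting Moxifloxacin for Ethambutol, of 24 weeks duration is superior to a control regimen".
- SAP 2: "Moxifloxacin-containing regimen, substituting Moxifloxacin for Ethambutol, of 24 weeks duration is superior to a control regimen of 24 weeks duration".

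Protocol 6.1 gives a single dosing basis for both arms: "The Control and Intervention arms will follow the South African National Tuberculosis dosing guidelines for re-treatment cases as closely as possible". Protocol Table 1 and the table in SAP 2 list the regimens as HRZM then HRM (intervention) and HRZE then HR (control).

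Tables 2 and 3 give tablet strengths and counts by weight. In the intensive phase the control arm takes a four-drug tablet, listed as "RHZE (150,75,400,275 mg". The intervention arm takes rifampicin/isoniazid tablets, separate 500 mg pyrazinamide tablets and one moxifloxacin tablet. Table 2 has four weight bands and Table 3 has three.

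SAP 1.1 and SAP 6.3 state the objective as one regimen against another and omit the substitution wording. SAP 6.3 compares culture conversion at the end of the intensive phase and at month 6. SAP 6.5 compares Grade 3 and 4 adverse events.

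**The concern.** A reader told that one drug replaces another will take isoniazid, rifampicin and pyrazinamide to be the same in both arms, and will credit or blame moxifloxacin in place of ethambutol for whatever difference appears. Tables 2 and 3 do not bear that out in the intensive phase, and the regimen lists do not bear it out in the continuation phase.

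Within a weight band, arm assignment fixes both the exchange of drugs and the companion doses. Neither randomisation nor regression adjustment can separate the two. What is at stake is the interpretation of the primary comparison and of the Grade 3/4 comparison. The first primary time point closes the phase in which companion doses differ. By month 6, up to four months of HRM against HR have been added. Protocol Table 4 lists liver damage and joint pain for pyrazinamide, so an excess of such events in the intervention arm would also have more than one candidate cause.

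No sentence in either document states that companion doses differ between arms, gives a reason, or carries the difference into interpretation.

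**Working it through.** **Inputs.** Table 2, control, intensive phase: R 150, H 75, Z 400 and E 275 mg per tablet; 2, 3, 4 and 5 tablets at 30-37, 38-54, 55-70 and >71 kg. Table 3, intervention, intensive phase: RH 150/75 mg × 2 or × 3 in the two lower bands and RH 300/150 mg × 2 above 55 kg; Z 500 mg × 2, 3 and 4; M 400 mg × 1.

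**Reading of the bands (assumption).** The >55 kg row of Table 3 is taken as 55 kg and up, and set against both Table 2 bands from 55 kg. As printed, exactly 55 kg has no row in Table 3, and weights above 70 kg up to 71 kg have no row in Table 2.

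**The plan's own counts.** 7 days × 8 weeks = 56 doses and 7 × 16 = 112 doses, as both tables state.

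**Daily intensive-phase dose = tablets × strength (intervention v control, mg).**

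| Weight (kg) | Pyrazinamide | Rifampicin | Isoniazid |
|---|---|---|---|
| 30-37 | 2×500 = 1000 v 2×400 = 800 | 300 v 300 | 150 v 150 |
| 38-54 | 3×500 = 1500 v 3×400 = 1200 | 450 v 450 | 225 v 225 |
| 55-70 | 4×500 = 2000 v 4×400 = 1600 | 600 v 600 | 300 v 300 |
| >71 | 4×500 = 2000 v 5×400 = 2000 | 2×300 = 600 v 5×150 = 750 | 2×150 = 300 v 5×75 = 375 |

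**Relative difference.**

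- Pyrazinamide up to 70 kg: 1000/800 = 1500/1200 = 2000/1600 = 1.25, or +25%.
- Above 71 kg: pyrazinamide 2000/2000 = 1.00; rifampicin 600/750 = 0.80; isoniazid 300/375 = 0.80, or -20% each.

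The ratios are the same per kg, because body weight cancels. No control-arm band has all three companion drugs matched.

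**Over the phase.** For a patient who stays in one band and takes exactly 56 doses, the pyrazinamide difference is 200 × 56 = 11.2 g, 300 × 56 = 16.8 g or 400 × 56 = 22.4 g. Above 71 kg it is 150 × 56 = 8.4 g less rifampicin and 75 × 56 = 4.2 g less isoniazid. These totals are conditional: weight is checked monthly and "the dose of the study product will be adjusted in accordance with" it, and the intensive phase may be extended.

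**Continuation phase.** Rifampicin is 300, 450, 600 and 600 mg and isoniazid 150, 225, 300 and 300 mg in both arms, so the differences are zero. Moxifloxacin is given in one arm and has no counterpart in the other.

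**The case against.** **The trial compares regimens, and the substitution wording only names the drug that changes.** Much of this stands. SAP 1.1 and 6.3, which govern the analysis, already compare regimens, and nowhere do the objectives say that a difference will be credited to moxifloxacin alone. But four passages describe the contrast as an exchange, and Protocol 6.1 gives both arms one dosing basis. A reader has no cue to expect different companion doses.

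**Nothing is hidden.** True: every strength and count is printed, and HRM v HR is stated openly. What is missing is a sentence that sets the two tables against each other.

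**Separate tablets explain the mismatch.** Protocol 6.3 says combination tablets are used where they can be, which explains why the arms use different tablets. Whole 500 mg tablets cannot make 800, 1200 or 1600 mg, so some gap is unavoidable with them. The ratios are 800/500 = 1.6, 1200/500 = 2.4 and 1600/500 = 3.2. Rounding to the nearest tablet gives 2, 2 and 3 (1000, 1000 and 1500 mg), whereas the printed counts are 2, 3 and 4. Always rounding up would give the printed counts, but neither document states such a rule. Tablet size also does not account for the rifampicin and isoniazid gap above 71 kg, where the two tables simply use different bands. Whatever its origin, the gap limits attribution in the same way.

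**Stronger readings a reader might infer.** One is that the randomised comparison is invalid. It is not: the arms are randomised to two regimens, and the test of those regimens as dosed is sound. A second is that the doses favour the intervention arm. The documents give no weight distribution and no dose-response relation, and the imbalance changes drug and direction above 71 kg. A third is that Table 3 is the deficient one. The tables differ; nothing shows which should give way.

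**Conclusion.** The point holds as a limit on attribution. As printed, intensive-phase companion doses differ in every control-arm weight band (+25% pyrazinamide up to 70 kg; -20% rifampicin and isoniazid above 71 kg), and in the continuation phase moxifloxacin is an addition. A difference in culture conversion at the end of the intensive phase or at month 6, or in Grade 3/4 events, therefore cannot be assigned to the one-for-one substitution alone. Matching the companion doses would not restore that reading at month 6, because HRM v HR would remain.

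The size and direction of any effect on conversion or event rates cannot be derived from the documents. The pharmacokinetic sub-study does not close the gap: it covers a subset and is framed around moxifloxacin and rifampicin-containing therapy, without naming pyrazinamide.

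The dose figures rest on Tables 2 and 3 as printed and on the band reading given with the calculation. The change is worth making because it costs little and alters what the trial may claim.

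**What to change.** 1. The clinical team should reconcile Tables 2 and 3 with each other and with the Schema, Protocol 2.1, 3.0 and 6.1 and SAP 2. No dose is proposed here.
2. If the differences stand, reword the Schema, Protocol 2.1 and 3.0 and SAP 2 so that the contrast is the two regimens as dosed. Name both departures from a pure exchange: the intensive-phase companion-dose differences and HRM v HR.
3. Leave the objective in SAP 1.1 and 6.3 as it is. Add one sentence to SAP 6.3 saying that a between-arm difference will not be attributed to the moxifloxacin-for-ethambutol substitution alone.
4. Optional: a descriptive table of isoniazid, rifampicin and pyrazinamide exposure by arm and weight band. SAP 6.1 to 6.8 plan none. The data are already collected: weight is recorded monthly, and the pharmacist and clinician "will monitor the number of doses ingested, by pill count, for each phase of treatment". The table would document the gap, but it cannot separate the effect of the swap from that of the companion doses.

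The cost is a few sentences and, if wanted, one table. Tests, sample size (330) and visits are unchanged. The downside is a narrower claim.

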**Table 1: Study Regimens**

Study Regimens		
	Intensive phase	Continuation phase
Intervention Arm *	HRZM daily (first 2 months )	HRM daily (4 months)
Control Arm **	HRZE daily (first 2 months )	HR daily (4 months )

H – Isoniazid; R – Rifampicin; Z – pyrazinamide; E – Ethambutol; M - Moxifloxacin

\* When patients become smear negative, they will be switched from the intensive phase to continuation phase with Isoniazid, Rifampicin and Moxifloxacin for 4 months

\*\*When patients become smear negative, they will be switched from the intensive phase to continuation phase with RIF and INH for 4 months.

In this study the total duration of TB therapy will be 24 weeks (6 months) for the Intervention Arm, and the Control Arm. The duration of TB treatment may increase due to a delay in the time to sputum conversion. This will result in the extension of TB treatment beyond 6 months.

### 3.1 Study setting: study site and populations

The study will be conducted at the CAPRISA eThekweni Clinical Research Site (eCRS), adjoining the largest government outpatient TB facilities, the Prince Cyril Zulu Communicable Disease Centre (PCZCDC). The PCZCDC provides free diagnosis and treatment for patients with TB in Durban. The clinic is readily accessible by public transport. Over the last 3 years, TB cases in the Durban region have increased by 38%. In 2001, 7,819 received TB care, 70% had pulmonary tuberculosis. In 2008, 4179 TB patients were managed at the clinic and of these, 2204 had smear positive TB. Approximately 35% of patients have a past history of TB. The majority (91%) of TB patients are black Africans, unemployed (53%), women (39%), 69% are HIV co-infected and the median age was 33 years (range: 5-72 years). The change in number from 2001 to 2008 is due to the decentralization of TB services. In order to make treatment even more accessible and also improve case holding. Laboratory support is available onsite.

## 4.0 INCLUSION AND EXCLUSION CRITERIA

### 4.1 Inclusion

- 4.1.1 Adults  $\geq$  18 years of age
- 4.1.2 Previous history of anti-TB chemotherapy
- 4.1.3 HIV status: HIV infected and uninfected patients are allowed in the study:
  - 4.1.3.1 All patients must agree to HIV testing to confirm HIV status.
  - 4.1.3.2 Patients already on ARVs will be allowed in the study provided that the ART regimen is not contraindicated with any of the study agents (see 4.2.1 below).
  - 4.1.3.3 HIV infected patients at any CD4 count irrespective of ART commencement and duration will be included in the study
- 4.1.4 Smear positive
- 4.1.5 Rifampicin susceptible as determined by Gene Xpert at screening. Gene Xpert will be used to determine Rifampicin resistance, hence the study team will be made aware of resistance prior to study enrolment.
- 4.1.6 Karnofsky score  $\geq$  70
- 4.1.7 Female candidates of reproductive potential must agree to use two reliable methods of contraception while on study: a barrier method of contraception (condoms or cervical cap) together with another reliable form of contraceptive (condoms with a spermicidal agent, a diaphragm or cervical cap with spermicide, an Intrauterine Device (IUD), or hormone-based contraceptive)
- 4.1.8 A negative pregnancy test
- 4.1.9 Laboratory parameters done at, or  $\leq$  14 days prior to, screening:
  - Haemoglobin level of at least 7.0 g/dL
  - Serum aspartate transaminase (AST) and alanine transaminase (ALT) activity less than 3 times the upper limit of normal
  - Serum total bilirubin level less than 2.5 times upper limit of normal
  - Creatinine clearance (CrCl) level greater than 60 ml/min
  - Platelet count of at least  $50 \times 10^9$  cells/L
  - Serum potassium greater than 3.0 mmol/L

### 4.2 Exclusion

- 4.2.1 Patients on a Nevirapine (NVP)-containing ART regimen at screening
- 4.2.2 Pregnant or breastfeeding
- 4.2.3 Received an antibiotic active against *M. tuberculosis* in the last 14 days (e.g. fluoroquinolones, macrolides, standard anti-tuberculosis drugs).
- 4.2.4 Patients with known *M. tuberculosis* resistance to any of the study drugs at screening
- 4.2.5 History of prolonged QT syndrome or current or planned therapy with quinidine, procainamide, amiodarone, sotalol, or ziprasidone during the intensive phase of tuberculosis treatment.
- 4.2.6 Known allergies or intolerance to any of the study drugs.

NOTE: All potential participants will undergo screening evaluations to determine eligibility. The site investigator (or designate) will assess eligibility and ensure that the participant meets all of the inclusion criteria.

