#### **6.5 Antiretroviral treatment and PCP prophylaxis**

Patients, who initiate the study whilst on antiretroviral therapy or during the course of the study require antiretroviral therapy, will be given a regimen that substitutes nevirapine with efavirenz. Patients found to be HIV infected may be given cotrimoxazole/dapsone prophylaxis in accordance with HIV/AIDS guidelines implemented locally.

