## 7. CLINICAL AND LABORATORY EVALUATIONS

### 7.1 Schedule of Events (SoE)

**Table 5: Study Table of Evaluations**

Procedures	Screening	Baseline	Week			Study Months														
			2	4	6	2	3	4	5	6	7	8	10	12	14-24 (*2 monthly)	End TB Treat	Recurr ence 	Termi nation	Time of IRIS	Time of Serocon version
Inclusion & Exclusion Criteria		X																		
Informed Consent	X																			
Randomization		X																		
HIV test (performed monthly for HIV negative participants)	X 		X			X	X	X	X	X	X	X	X	X	X	X	X	X	X	X
Medical , Medication and TB History & Physical Exam	X	X	X			X	X	X	X	X	X	X	X	X	X	X	X	X	X	X
Vitals (including Pregnancy test )	X	X	X			X	X	X	X	X	X	X	X	X	X	X	X	X	X	X
Contraception confirmation	X	X	X			X	X	X	X	X	X	X	X	X	X	X	X	X		
Concomitant medications	X	X	X			X	X	X	X	X	X	X	X	X		X				
GeneXpert	X																			
Sputum Smear	X	X	X			X	X	X	X	X	X	X	X	X	X	X	X	X		
Culture : INTERVENTION ARM: until 6 months		X	X	X	X	X	X	X	X	X					X	X	X			
Culture: CONTROL ARM: until 6 months		X	X	X	X	X	X	X	X	X					X	X	X			
Susceptibility		X				X				X*		X*				X	X			
PAXgene for SHIP Study		X				X				X		X			X	X	X	X		
Urine (Lam Testing)		X				X			X	X						X				
Chest radiograph		X 					X			X						X	X			
ECG **		X				X		X		X										
Vision testing (Snellen and Ishihara) Control Arm only		X				X														

Procedures	Screening	Baseline	Week			Study Months											End TB Treatment	Recurrence	Termination	Time of IRIS	Time of Seroconversion
			2	4	6	2	3	4	5	6	7	8	10	12	14-24 (*2 monthly)						
AST, ALT, Bilirubin, Hb, platelets, & Full blood count, Creatinine clearance, potassium, total protein, alkaline phosphatase and as clinically indicated	X	X 				X		X		X							X	X	X	X	X
CD4 Count ( HIV Infected patients only )	X					As per SA HIV guidelines														X	
Viral Load ( HIV Infected patients only )	X																	X		X	
HBsAg	X																				
PK Samples (Intervention Arm)				X		X 3				X	X 										
PK Samples (Control Arm)						X															
Specimen Storage		X	X		X		X						X				X				X
PBMCs***		X 				X				X					X	X	X	X	X	X	X

1: HIV Testing is required at screening for all potential participants. Thereafter, HIV testing will be required for HIV negative participants only as per SoE above.

2: A chest radiograph/Bloods will be repeated if they are more than 14 days old

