#### Study visits – continuation phase of therapy

Intervention arm - study visits Month 3 to Month 6 will be considered as continuation phase.

Control arm - study visits Month 3 to Month 6 will be considered as continuation phase.

Month 4 – Patients will have an assessment for toxicity from the four-drug phase of therapy. This will consist of a symptom-driven examination, and laboratory testing (complete blood count and serum AST, total bilirubin, and serum creatinine). A sputum specimen will be obtained for culture.

Month 4-6–Patients will continue to have study visits monthly during the continuation phase of therapy. Sputum cultures will be obtained at Month 4, Month 5, Month 6 during the continuation phase of therapy. Laboratory testing, other than sputum cultures, will be at the discretion of the principal investigator/study clinician.

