#### *7.2.4 Study Visit Window and Unscheduled Visits*

The window period for all scheduled monthly study visits  $\pm 7$  days. Any visit for which a patient attends outside of the specified visit window but not in addition to those required as per the ‘schedule of evaluations’ should be considered as an early/late visit. The assessments which are undertaken as part of an early/late visit should reflect those for the visit which will be or has been missed. Any additional assessments should be undertaken as clinically indicated.

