## 8.0 CLINICAL MANAGEMENT ISSUES

### 8.1 Clinical Management Issues

The IMPRESS study will use the Division of AIDS Table for Grading the Severity of Adult and Paediatric Adverse Events (DAIDS AE Grading Table) Version 1.0, December 2004 (Clarification, August 2009)

- Patients need to be assessed for evidence of musculoskeletal toxicity at every study visit through history taking and physical examination.
- Ocular toxicity will be assessed using the Snellen and Ishihara tests at baseline and month 2 and/or when clinically required (Control Arm only). Patients will be educated about symptoms of ocular toxicity before treatment initiation, and will be assessed for ocular toxicity for the duration of TB therapy when Ethambutol forms part of the TB regimen. The Snellen and Ishihara tests will be repeated if any symptoms of ocular toxicity or any change in vision occurs.

- All patients will undergo ECG monitoring at baseline, Month 2, Month 4, Month 6 (and 2 monthly whilst being administered with Moxifloxacin). This will be repeated if patients complain of chest pain or syncope. Moxifloxacin will be substituted for Ethambutol if there is evidence of QT prolongation, or if patients QRS complexes change in amplitude from baseline.
- Patients must not have evidence of severe or life-threatening liver disease at baseline (Bilirubin, AST and ALT < 5 times the ULN), no evidence of renal impairment i.e. creatinine clearance of > 60 mls/min, serum potassium of > 3.0 mmol/l.

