## **Discontinuation of study treatment**

The investigator may discontinue a patient from treatment in the event of a severe or serious adverse event, or at any time he/she thinks it's in the patient's best interest. If there is a medical reason for withdrawing study treatment, the patient will remain under the supervision of the investigator until satisfactory health has returned irrespectively of the reason for discontinuation. The frequency of patient review will be determined by the clinical need to ensure optimal care.

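### The exclusion of five QT-prolonging drugs covers only the intensive phase, while moxifloxacin continues daily for 16 more weeks with no on-study rule against starting them

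*Protocol*

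**What the plan says.** Exclusion 4.2.5 of the protocol has two parts. A history of prolonged QT syndrome excludes a patient with no limit of phase. The co-medication part excludes "current or planned therapy with quinidine, procainamide, amiodarone, sotalol, or ziprasidone during the intensive phase of tuberculosis treatment".

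Tables 1 and 3 give the intervention arm one 400 mg moxifloxacin tablet daily in both phases and in every weight band: 56 intensive doses over 8 weeks, then 112 continuation doses over 16 weeks. Treatment may be extended if sputum conversion is delayed.

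Elsewhere the protocol treats QT risk as lasting as long as moxifloxacin is taken. Section 8.1 and the footnotes to Table 5 call for ECGs at baseline and Months 2, 4 and 6, and every two months while on moxifloxacin. The QTc rules in section 8.5 have no phase limit.

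For medication review, Table 5 has a row for "Concomitant medications" that includes Months 3 to 6, and section 7.2.3 says patients "will continue to have study visits monthly during the continuation phase of therapy". Section 7.2.4 sets a window of ±7 days around each monthly visit.

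Table 4 lists possible interactions with moxifloxacin. None of the five drugs in 4.2.5 is among them.

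**The concern.** The restriction on the five drugs ends when the intensive phase ends, but exposure to moxifloxacin does not. Followed as written, 4.2.5 admits a patient who is already scheduled at screening to begin, say, amiodarone in Month 4, and that patient could then be taking both drugs. A clinician considering such a drug in the continuation phase would find no warning in 4.2.5, in Table 4 or in any on-study rule in the supplied text.

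What is at stake is patient safety in the intervention arm: an avoidable overlap of two QT-prolonging drugs. No effect on the endpoint, power, analysis or balance between arms is claimed.

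**Working it through.** **Inputs.** Intensive phase 56 daily doses and continuation phase 112 daily doses (protocol Table 3); total treatment 24 weeks (6.1); visit window ±7 days (7.2.4); ECGs two-monthly (8.1); 330 patients (9.1), allocated 1:1 (SAP section 2).

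**Planned durations.** These reproduce the protocol's figures.
- Intensive: 56 / 7 = 8 weeks.
- Continuation: 112 / 7 = 16 weeks.
- Total: (56 + 112) / 7 = 168 / 7 = 24 weeks.

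**Share of planned moxifloxacin exposure.**
- Inside the 4.2.5 window: 56 / 168 = 33.3%.
- Outside it: 112 / 168 = 66.7%, plus any extension of the continuation phase.
- Delayed sputum conversion lengthens the intensive phase, and with it the window, so 8 weeks is the planned length and not a fixed one.

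**Who falls in the gap.** Patients already on one of the drugs at entry are excluded, and so are those with a QT history. Two groups remain:
- (a) therapy planned at screening to start after the intensive phase;
- (b) an unplanned new start during the continuation phase.

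An eligibility criterion can deal with (a) only; (b) needs an on-study rule. Only the intervention arm is exposed, about 330 / 2 = 165 patients. The documents do not say how many of them would fall in (a) or (b).

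**How soon an overlap would be noticed on schedule.**
- Medication review: 28 days between monthly visits. With one visit 7 days early and the next 7 days late, 28 + 7 + 7 = 42 days (6 weeks). With a calendar month of 30.5 days, 30.5 + 14 = 44.5, about 45 days.
- If starts are spread evenly between visits (an assumption), the mean wait is 28 / 2 = 14 days.
- ECG, the slower check: 56 days between recordings, up to 56 + 14 = 70.
- The continuation phase has four scheduled medication reviews (Months 3 to 6) and two scheduled ECGs (Months 4 and 6).

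**Comparison with nevirapine.** Nevirapine has an entry exclusion (4.2.1) and also an on-study rule: under section 6.5, patients who "during the course of the study require antiretroviral therapy, will be given a regimen that substitutes nevirapine with efavirenz". The five QT drugs have only the entry exclusion.

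**The case against.** The strongest case against is that the protocol already manages QT risk throughout treatment:
- 8.1 repeats the ECG for chest pain or syncope, so detection is not tied to the two-monthly schedule, and it provides for a switch between moxifloxacin and ethambutol on QT prolongation.
- 8.3.3 says that, for Grade 3 and 4 events, suspected concomitant drugs should be withheld first where possible.
- 8.4 makes asymptomatic QT prolongation associated with moxifloxacin reportable.
- 8.5 asks for twice-weekly QTc checks after Grade 2 prolongation attributed to study medication. At Grade 3 all study drugs stop and the patient is referred to hospital; at Grade 4 the patient is hospitalised and study medication stops. A likely causative concomitant drug is to be stopped.
- The discontinuation rule needs no adverse event: "The investigator may discontinue a patient from treatment in the event of a severe or serious adverse event, or at any time he/she thinks" it is in the patient's interest.

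All of this stands and lowers the severity. Most of these rules, however, act only once symptoms or QTc prolongation have appeared, and the last is discretionary. None says in advance that the five drugs should not be started while moxifloxacin is being taken.

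Several further points are fair. The 67% describes exposure, not patients at risk, and the group is likely to be small; the study clinic's median age is 33 (3.1). An ECG schedule and an entry criterion do different jobs, so the mismatch in period is not a contradiction. Nevirapine is not a like-for-like comparison, because 69% of the clinic's patients are HIV co-infected and antiretroviral treatment on study is routine. A protocol sentence does not bind prescribers outside the study, so for their prescriptions detection would still come at the next visit. Finally, some pages were removed before review, so the absence of a rule is established only for the supplied text.

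These points limit the size of the concern. They do not change the fact that 4.2.5, which is supplied in full, admits group (a).

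**Conclusion.** The concern holds, as a minor patient-safety gap in wording. The co-medication exclusion covers 8 of the 24 planned weeks of moxifloxacin, and nothing in the supplied text bars starting the five drugs in the other 16. It matters only for late starts planned at screening and for unplanned new starts in the intervention arm. If one occurs, the clinician can act at the next monthly medication review, usually within about 4 weeks and at most about 6, possibly before any QTc change.

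This rests on the planned phase lengths, on monthly visits being kept within their windows, and on no relevant rule standing on the removed pages. The number of patients affected cannot be estimated from the documents.

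**What to change.** Three short edits:

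1. In 4.2.5, replace the restriction to the intensive phase with: at any time during study TB treatment, including any extension. This closes group (a) and widens the planned window from 8 weeks (56 doses) to 24 weeks (168 doses).
2. In the QTc part of section 8.5, or beside Table 4, add: the drugs listed in 4.2.5 are not to be started while a participant is taking moxifloxacin; if one becomes necessary, the clinician first decides whether to stop or replace moxifloxacin. Check this at each visit against the concomitant-medication record already collected. This addresses group (b), at least for prescribing that the study team controls or learns of.
3. In 7.3.6, add one line making the same check before the optional single moxifloxacin dose at Month 7. It belongs in the PK procedure and not in main-trial eligibility.

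Cost: no new data collection, and no change to sample size (330), power or analysis. The few patients with such therapy planned after Month 2 would be excluded, including some who would have been allocated to control. A participant who comes to need one of these drugs would require a clinician's decision on moxifloxacin. If treatment is already complete, which the documents do not state, the sponsor can check the recorded concomitant medications for overlap instead.
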